2.4.4.3 Multiplicity issues

To control the Type I error, a step-down testing procedure (please see [Figure 1](#)) will be applied.

[figure not shown]
For the primary efficacy endpoint (change from baseline to Week 26 in HbA_{1c}), no multiplicity adjustment is needed to control the Type I error since only one comparison of FRC versus GLP-1 receptor agonist will be performed.

If the primary variable is statistically significant at the 5% level, a hierarchical testing procedure will be performed to test the following secondary efficacy variables in the following prioritized order. Testing will stop when an endpoint is found not to be statistically significant at the 5% level:

1. Percentage of patients reaching HbA_{1c} <7% at Week 26.
2. Change in FPG from baseline to Week 26.
3. Change in the daily average of the 7-point SMPG from baseline to Week 26.
4. Change in 2-hour Post Prandial Glucose (PPG) and/or glucose excursion during the standardized meal test from baseline to Week 26.

Multiplicity adjustment will not be performed on the secondary efficacy variables that are not included in the above list.

Figure 1 - The step-down testing procedure

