- Percentage of patients with GLP-1 receptor agonist use by type [QD/BID formulations (Victoza® or Byetta®), QW formulations (Bydureon®, Tanzeum®, or Trulicity®)] at screening;
- Daily dose of GLP-1 receptor agonist (Victoza® or Byetta®) at baseline, or weekly dose of GLP-1 receptor agonist (Bydureon®, Tanzeum, or Trulicity®) at baseline;
- Percentage of patients who used pioglitazone at screening (data from e-CRF);
- Percentage of patients who used SGLT2 inhibitor at screening (data from e-CRF);
- Duration of metformin treatment (years) derived as: (Date of informed consent – Date of first dose of metformin + 1)/365.25;
- Daily dose of metformin (mg) at baseline;
- Daily dose of pioglitazone (mg) at baseline (if used);
- Daily dose of SGLT2 inhibitor (canagliflozin, empagliflozin or dapagliflozin) at baseline (if used);
- Categorized daily dose of metformin at baseline (<1500, ≥1500 to <2500, ≥2500 to <3000, ≥3000 mg);
- Baseline diabetic microvascular complications (Yes, No) (ie, diabetic retinopathy, diabetic proliferative retinopathy, diabetic neuropathy, and diabetic nephropathy);
- Baseline urine albumin/creatinine ratio categories (<30 mg/g [Normal], ≥30 to <300 mg/g [Microalbuminuria], and ≥300 mg/g [Macroalbuminuria]);
- Estimated Glomerular Filtration Rate (eGFR) at screening (ml/min/1.73m²);
- eGFR categories at screening (<15 ml/min/1.73m² [End stage renal disease], ≥15 to <30 ml/min/1.73m² [Severe decrease in GFR], ≥30 to <60 ml/min/1.73m² [Moderate decrease in GFR], ≥60 to <90 ml/min/1.73m² [Mild decrease in GFR], and ≥90 ml/min [Normal]).

Baseline efficacy variables

The baseline efficacy variables include:

- HbA1c;
- During standardized meal test:
 - 2-hour postprandial plasma glucose (PPG) and glucose excursion;
 - C-peptide under fasting (30 minutes prior to the meal test before IMP administration if IMP is injected before breakfast), just before the start of the standardized meal (0 minute), 30 minutes, 1-hour, 1.5-hour, and 2-hour postprandial conditions;

Note: 2-hour plasma glucose excursion= 2-hour post prandial plasma glucose value – plasma glucose value obtained 30 minutes prior to the start of meal and before IMP administration if IMP is injected before breakfast. C-peptide under 1.5-hour postprandial condition is only for patients enrolled after the approval of Protocol Amendment 1.

- 7-point (average and each time point) SMPG;
- Body weight;
- Fasting plasma glucose (by central laboratory).

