2.1.3.2 Secondary efficacy endpoint(s)

Continuous secondary efficacy endpoints

The continuous secondary efficacy endpoints are:

- Change in FPG from baseline to Week 26,
- Change in 7-point SMPG profiles from baseline to Week 26 (each time point and average daily value),
- Change in 2-hour PPG and in blood glucose excursion during standardized meal test from baseline to Week 26,
- Change in body weight from baseline to Week 26,

7-point SMPG profiles will be analyzed based on the average of the glucose values recorded on eCRF on 2 different days in the week prior to the scheduled visits.

For 7-point SMPG profiles, the mean daily (ie, average on 7 points) change from baseline to Week 26 will be analyzed. In addition, the change from baseline to Week 26 for each of the 7 points will be evaluated, respectively.

For FPG, only values assessed in fasting condition will be analyzed.

Categorical secondary efficacy endpoints

The categorical secondary efficacy endpoints are:

- Percentage of patients reaching HbA1c $\leq 6.5\%$ (49 mmol/mol) at Week 26,
- Percentage of patients reaching HbA1c $< 7\%$ (53 mmol/mol) at Week 26.
- Percentage of patients requiring rescue therapy during the 26-week randomized treatment period.

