2.4.4.2 Analyses of secondary efficacy endpoints

For secondary efficacy endpoints included in the multiplicity procedure described in [Section 2.4.4.3](#), 2-sided statistical tests for the superiority of FRC over GLP-1 receptor agonist will be performed at the alpha level of 0.05.

Except for 2-hour PPG and glucose excursion, all continuous secondary efficacy endpoints at Week 26 defined in [Section 2.1.3.2](#) will be analyzed using the same MMRM approach as described in [Section 2.4.4.1](#) to compare FRC with GLP-1 receptor agonist. The analyses include all scheduled measurements collected during the 26-week randomized treatment period, including those obtained after IMP discontinuation or introduction of rescue therapy. This model will include fixed effect terms including treatment group (FRC or GLP-1 receptor agonist), randomization strata of HbA_{1c} (<8%, ≥8%) at V1 (week -2), randomization strata of GLP-1 receptor agonist subtype (QD/BID formulations, QW formulations) at screening, scheduled visit, treatment-by-visit interaction, and world region, and the covariate of baseline value-by-visit interaction. Means and adjusted means of each treatment group will be provided, as well as adjusted mean and associated two-sided 95% CI of the differences between treatment groups. The statistical tests for between-group differences will be two-sided at the alpha level of 0.05.

2-hour PPG and glucose excursion, for which only 1 post-baseline assessment is scheduled, will be analyzed using ANCOVA with the missing data at Week 26 imputed by LOCF to compare FRC with GLP-1 receptor agonist. This model will include fixed effect terms including treatment group (FRC or GLP-1 receptor agonist), randomization strata of HbA_{1c} (<8%, ≥8%) at V1 (week -2), randomization strata of GLP-1 receptor agonist subtype (QD/BID formulations, QW formulations) at screening, and world region, and a covariate using the corresponding baseline value. Means and adjusted means of each treatment group will be provided, as well as adjusted mean and associated two-sided 95% CI of the difference between treatment groups. The LOCF procedure will be used by taking the last available post-baseline measurement collected during the 26-week randomized treatment period as the value at Week 26.

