For all continuous secondary endpoints, only descriptive statistics will be provided for the FRC group at the scheduled visits for the whole study period including the extension period. For all the categorical secondary endpoints defined for the extension period, counts and percentages will be summarized for FRC group using all data available at Week 52, with patients having data missing at Week 52 treatment as non-responders.

Sensitivity analysis

Sensitivity analyses will be performed for the following variables using scheduled measurements collected during the 26-week on-treatment period (excluding those collected after introduction of rescue therapy) (see [Section 2.1.3](#)). Continuous variables will be analyzed using MMRM or ANCOVA depending on the variables as specified earlier in [Section 2.4.4.2](#). Categorical variables will be analyzed using CMH method as described earlier. For the categorical variables in which HbA1c is assessed at Week 26, patients will be treated as failures (non-responders) if they have no assessment during the on-treatment period, including those who discontinue study treatment before Week 26, start rescue therapy before Week 26, or have no on-treatment assessment at all in mITT population.

- Change in 2-hour PPG and in glucose excursion during the standardized meal test from baseline to Week 26,
- Change in the daily average of the 7-point SMPG from baseline to Week 26 (each time point and average daily value),
- Change in FPG from baseline to Week 26,
- Change in body weight from baseline to Week 26,
- Percentage of patients reaching HbA1c $\leq 6.5\%$ at Week 26,
- Percentage of patients reaching HbA1c $< 7\%$ at Week 26.

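### Does the *and/or* in the last step of the testing hierarchy leave the 5% error rate, or the final claim, undefined?

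*SAP*

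**What the plan says.** SAP 2.4.4.3 and Protocol 11.4.4.3 give the same fixed sequence after the primary test: HbA1c below 7%, FPG, daily average of the 7-point SMPG, and then "Change in 2-hour Post Prandial Glucose (PPG) and/or glucose excursion during the standardized meal test from baseline to Week 26". The stopping rule is written for one endpoint per step: "Testing will stop when an endpoint is found not to be statistically significant at the 5% level". The SAP adds "Multiplicity adjustment will not be performed on the secondary efficacy variables that are not included in the above list".

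Elsewhere the same pair is joined differently. The endpoint list in SAP 2.1.3.2 has "Change in 2-hour PPG and in blood glucose excursion during standardized meal test from baseline to Week 26", and the sensitivity list in SAP 2.4.4.2 has "Change in 2-hour PPG and in glucose excursion during the standardized meal test from baseline to Week 26". SAP 2.4.4.2 sets the analysis: "2-hour PPG and glucose excursion, for which only 1 post-baseline assessment is scheduled, will be analyzed using ANCOVA", each variable with its own baseline as covariate, so there are two p-values. For listed endpoints, "2-sided statistical tests for the superiority of FRC over GLP-1 receptor agonist will be performed at the alpha level of 0.05". SAP 2.1.1 defines the second variable from the first: "2-hour plasma glucose excursion= 2-hour post prandial plasma glucose value" minus the plasma glucose taken 30 minutes before the meal.

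Both documents refer to Figure 1 for the procedure. It is not shown in the text available here. SAP 1.6 Table 2 records that test numbers were added to it. SAP Appendix C, the summary of statistical analyses, was not available either.

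**The concern.** A fixed sequence protects the error rate because each step has one hypothesis and one verdict. Here the last step has two hypotheses and a conjunction that can mean either or both. Three things could go wrong.

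- If *or* is meant and each variable is tested at full 5%, the step taken alone rejects too often.
- If only one variable is significant, the list does not say whether step 4 passed, so the reading could be picked once both p-values are known.
- Because unlisted variables get no adjustment, it matters whether excursion is in the list, and *and/or* leaves that open.

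A split result is plausible. If treatment lowers fasting glucose and 2-hour PPG together, PPG can be significant while excursion, which subtracts the fasting part, is not. What is at stake is the confirmatory label on one or two meal-test variables.

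**Working it through.** **The plan's own figure.** The only power figure is 250 per group for the primary endpoint. With 20% of FRC patients assumed to respond as control, the effect is 0.8 × 0.4 = 0.32, and n = 2 × (1.960 + 1.282)² × 1.1² / 0.32² ≈ 249 per arm; the exact t-test needs 250. It reproduces, but it says nothing about step 4. The documents give no power, variance or correlation for the meal-test variables, so those below are assumptions.

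**Correlation of the two step-4 tests.** Let E = P − F, with P the 2-hour PPG, F the pre-meal fasting value, k the ratio of the standard error of P to that of F, and r the correlation of F and P. Then

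corr(P, E) = (k − r) / √(k² + 1 − 2rk).

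For k = 1.25, r = 0.7: 0.55 / √0.8125 = 0.61. For k = 2, r = 0.7: 1.3 / √2.2 = 0.88. Over k = 1.25 to 2.0 and r = 0.3 to 0.7 the range is 0.61 to 0.88.

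**Either-wins step taken alone, both nulls true.** The two-sided error is 1 − P(|Z₁| < 1.96 and |Z₂| < 1.96). At correlation 0 it is 1 − 0.95² = 9.75%. Over the range above it is 8.7% (0.61) to 7.2% (0.88). This is what makes the wording look serious, but it assumes that step 4 has already been reached.

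**The gate.** Since E = P − F, the difference between arms in F equals the difference in P minus the difference in E. Two cases follow.

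- Both step-4 nulls true: the fasting difference is also zero. Step 2 then tests a true null and lets testing continue in at most 5% of trials, so a false claim at step 4 cannot exceed 5%. Simulation gated on FPG alone (|z| > 1.96, with the FPG analysis correlated 1.0 or 0.8 with the meal-test fasting value) gives 0.7 to 1.9% two-sided and 0.2 to 0.8% in the FRC direction. The primary test and steps 1 and 3 would lower this further.
- A real fasting effect: at most one step-4 null is true, so only that variable can be claimed falsely, on its own 5% test. Simulation with a fasting effect of 3.24 or 8 standard errors gives 3.3 to 5.0% two-sided and 1.5 to 2.5% in the FRC direction.

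The gate and step 4 are close in the data too: Protocol 1.2 (footnote j) and 9.2.1.2.6 make the Week 26 FPG part of the same meal test.

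**Stricter readings.** Requiring both has, taken alone with both nulls true, an error of 1.25% at correlation 0.6 and 3.0% at 0.9. Testing PPG then excursion, or the reverse, is at most 5%.

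**How often the readings give different verdicts.** Illustration under assumed powers for PPG/excursion, gated on FPG in the FRC direction, with the FPG analysis taken as the meal-test fasting value:

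| Power PPG/excursion | Verdicts differ, given FPG passes | FPG passes and verdicts differ |
|---|---|---|
| 90%/50% | 41–68% | 20–39% |
| 90%/80% | 13–54% | 2.5–8.6% |
| 90%/90% | 5–46% | 0.5–2.7% |

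The last column is small in the lower rows because high power for excursion implies little fasting effect (−0.3 to 1.7 standard errors at 90%/90%), so step 2 seldom passes.

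**The case for a change.** The strongest case for a change is about pre-specification rather than inflation. In the 90%/50% setting a split result at step 4 is a real prospect, and a hierarchy should state the verdict before the p-values are known. The SAP does this for its composite of HbA1c below 7% with no weight gain, where it says in 2.4.4.4 that each component must be met; step 4 has no such sentence. Naming a rule would cost one line. This stands as a comment on drafting.

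The link between the gate and step 4 is also not exact. FPG is analysed by MMRM with values after rescue included. The meal test is done before rescue, is not repeated at the final visit, and is carried forward by LOCF. Its baseline comes from Visit 2, while FPG is also drawn at Visit 3. If these differences were large enough for FPG to show an effect while both meal-test nulls held, an either-wins step would have the 7.2 to 8.7% two-sided error computed above, or about 3.6 to 4.4% in the FRC direction against a nominal 2.5%. That needs a true FPG effect with no fasting difference at all in the meal-test data, which is hard to picture when the two share the Week 26 draw.

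Against a change, both documents define the procedure by a figure that could not be seen, and that figure carries test numbers. It or Appendix C may already separate or order the two variables, and content not shown here cannot be counted as missing from the plan.

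**Conclusion.** The observation about the wording is correct, but it does not call for a change. The most permissive reading, each variable claimed on its own p-value once FPG has passed, keeps the false-claim rate at or below about 5%: 0.7 to 1.9% with both nulls true, 3.3 to 5.0% with a real fasting effect and one null true. The stricter readings are within 5% as well. An analyst can therefore adopt any sensible reading without harm to the error rate. SAP 2.4.4.2 has both variables analysed by the same ANCOVA with an adjusted difference and 95% CI, so a split result would be visible whatever label step 4 receives.

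The effect is confined to the last step. Nothing is tested after it, and the primary endpoint, steps 1 to 3 and the sample size do not depend on it.

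The 5% bound rests on excursion being PPG minus the fasting value, and on the FPG analysis tracking that fasting value closely. The narrower ranges also depend on the assumed k, r and effect sizes. This is a gap in detail that Figure 1 or Appendix C may already fill.

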2.4.4.4 Additional efficacy analysis(es)

For the daily insulin glargine and lixisenatide doses, summary statistics at scheduled visits (using OC) will be provided for the FRC group. The summary will include the number of observations, mean, SD, minimum, median, and maximum. Summary statistics will also be provided for the body weight adjusted insulin glargine doses at scheduled visits (using OC). In addition, daily dose of insulin glargine at scheduled visits (using OC) will be summarized by count and percentage for each of these categories: <10 U, ≥10 U - <20 U, ≥20 U - <30 U, ≥30 U - ≤ 40U, > 40 U - ≤ 50; >50 to ≤ 60U, =60U, and > 60 U. Daily dose of lixisenatide at scheduled visits (using OC) will be summarized by count and percentage for each of these categories: <5 µg, ≥5 µg- < 10 µg, ≥10 µg- <15 µg, ≥15 µg- ≤ 20µg, = 20µg, > 20µg.

Number and percentage of patients at scheduled visits (using OC) by pen type (Peach 2:1, Olive 3:1) will be provided. Patients' pen use status during the 26-week randomized treatment period will also be summarized by count and percentage for each of these categories: No switch of pen, switch pen once from Peach 2:1 to Olive 3:1 at any time, and other patterns.

Number and percentage of patients in the FRC group will also be summarized by pen type and the dose categories described above based on the final doses of insulin glargine and lixisenatide at the end of the 26-week randomized treatment period, respectively.

For the C-peptide evaluation, summary statistics (for screening value, baseline value, observed values, and observed changes from baseline) at scheduled visits (using OC) will be provided for each treatment group. Each summary will include the number of observations, mean, SD, minimum, median, and maximum. A summary statistics table will also be presented using assessments obtained during the 26-week on-treatment period (see [Section 2.1.3](#)).

The following categorical variables will be summarized using count and percentage by treatment group.

- Percentage of patients reaching HbA_{1c} <7% (53 mmol/mol) with no body weight gain at Week 26.
- Percentage of patients with no body weight gain at Week 26.
- Percentage of patients reaching the fasting SMPG target (≤ 100 mg/dl) at Week 26 (for the FRC group only).

For the categorical variables in which HbA_{1c}, body weight or fasting SMPG is assessed at Week 26, all values at Week 26 will be used to determine whether a patient is a responder or not, even if they are measured after IMP discontinuation or introduction of rescue therapy. If no assessment is available at Week 26 at all, patients will be treated as failures (non-responders).

Similar summary tables will also be presented using scheduled measurements collected during the 26-week on-treatment period (see [Section 2.1.3](#)) in mITT population. Patients will be treated as failures (non-responders) if they have no such assessments during the 26-week on-treatment

period, including those who discontinue study treatment before Week 26, start rescue medication before Week 26, or have no on-treatment assessments at all in mITT population.

For the composite endpoint (HbA1c <7% with no body weight gain), a patient will be treated as a responder only if the criterion is met for each component of the composite endpoint.

For the FRC group only, selected analyses of other endpoints defined in [Section 2.1.3.3](#) will also be performed for the whole study including the 26-week single-arm extension period (using assessment obtained during whole study and/or the on-treatment period of the whole study defined in [Section 2.1.3](#)).

2.4.5 Analyses of safety data

The summary of safety results will be presented by treatment group for the 26-week randomized treatment period, unless specified otherwise. A similar summary of safety results will also be presented for FRC group for the whole study treatment period including the 26-week single-arm extension period, as appropriate.

The “observation period” defined in [Section 2.1.4](#) are applicable for classification of AEs, (potentially clinically significant abnormality) PCSA values for the laboratory and vital sign.

General common rules

All safety analyses will be performed on the safety population as defined in [Section 2.3.2](#), unless otherwise specified, using the following common rules:

- Safety data in patients who do not belong to the safety population (eg, exposed but not randomized) will be listed separately;
- The baseline value is defined as the last available value before the first injection of open-label IMP. For WBC and differential counts, the baseline will be defined as the last available value before the first injection of open-label IMP where no differential component is missing;
- The PCSA values are defined as abnormal values considered medically important by the Sponsor according to predefined criteria/thresholds based on literature review and defined by the Sponsor for clinical laboratory tests, vital signs, and ECG (PCSA version dated May 2014 [[Appendix A](#)]). PCSA criteria for parameters not cited in the protocol as safety parameters will not be analyzed;
- PCSA criteria will determine which patients had at least 1 PCSA during the specified period, taking into account all evaluations performed during the specified period, including unscheduled or repeated evaluations. The number of all such patients will be the numerator for the PCSA percentage during the specified period;
- The treatment-emergent PCSA denominator by group for a given parameter will be based on the number of patients assessed for that given parameter during the specified period by treatment group in the safety population;

- For laboratory parameters cited in the protocol as efficacy endpoints (including HbA1c and plasma glucose), PCSA summaries will not be provided. These parameters will be summarized in [Section 2.4.4](#);
- For quantitative safety parameters based on central laboratory/reading measurements, descriptive statistics will be used to summarize results and change from baseline values by visit and treatment group. Summaries will include the last on-treatment value (see [Section 2.5.4](#));
- The analysis of the safety variables will be descriptive and no testing is planned;
- Selected safety analyses will be summarized by age group (<50, ≥50 to <65, ≥65 to < 75, ≥75 years of age), gender, race subgroups, GLP-1 receptor agonist subtype at screening, and any pertinent subgroups as appropriate.

2.4.5.1 Analyses of symptomatic hypoglycemia

Analyses of symptomatic hypoglycemia will be performed on the on-treatment period, as defined in [Section 2.1.4](#). Unless specified otherwise, all analyses described below will be performed by treatment group for the 26-week on-treatment period and for FRC group for the on-treatment period of the whole study including the extension period, respectively.

The number (%) of patients with any symptomatic hypoglycemia recorded in the dedicated eCRF “Symptomatic hypoglycemia” page and meeting protocol definitions for severe, documented or probable symptomatic hypoglycemia described in [Section 2.1.4.1](#) and with at least 1 symptomatic hypoglycemia by category (ie, severe, documented, and probable symptomatic hypoglycemia) will be summarized by treatment group for the on-treatment period, as well as the incidence rate in patient years. Two types of incidence rates will be presented: the number of patients with at least 1 event per patient years (calculated as the number of patients with at least 1 event / total exposure in patient years), and the number of events per patient years (calculated as the number of events / total exposure in patient years). Note: here exposure is duration of on-treatment, ie, duration of IMP treatment in days +1 for daily formulation and duration of IMP treatment in days + 7 for weekly formulation (see [Section 2.1.4](#)).

The above summary will also be provided for the on-treatment period before introduction of rescue therapy. In addition, all the above summary will be provided for documented symptomatic hypoglycemia with plasma glucose <60 mg/dL [3.3 mmol/L].

- The summary of frequency and incidence rate in patient years for documented symptomatic hypoglycemia will be provided as appropriate by gender (Male, Female), age group (<50, ≥50 to <65, ≥65 to < 75, ≥75 years of age), race (American Indian or Alaska Native, Asian/Oriental, Black, Native Hawaiian or Other Pacific Islander, White, Other), GLP-1 receptor agonist subtype (QD/BID formulations, QW formulations) at screening, SGLT2 inhibitor use (Yes, No) at screening (if each category contains sufficient number of patients), and insulin and lixisenatide dose groups (FRC group only).
- The summary of frequency and incidence rate in patient years for documented symptomatic hypoglycemia will be provided by anti-lixisenatide and anti-insulin glargine

antibody status (Positive, Negative) during 26-week randomized treatment period and during whole study treatment period including 26-week extension period, respectively. A patient is defined as anti-lixisenatide (or anti-insulin glargine) antibody positive during the 26-week randomized treatment period (or whole study treatment period) if the patient is anti-lixisenatide (or anti-insulin glargine) antibody positive at any time during the 26-week randomized treatment period (or whole study treatment period).

The number (%) of patients with at least 1 documented symptomatic hypoglycemia during the 26-week on-treatment period will be assessed by treatment group over time, using weekly time intervals up to 26 weeks, ie, [0-1] week, (1-2] weeks, (2-3] weeks, (3-4] weeks, etc. Similar summaries will be provided for FRC group during the on-treatment period of the whole study, using weekly time intervals up to 52 weeks. In each time interval, the numerator in the calculation of percentages will be the number of patients with at least 1 event occurring in this time interval. Two types of analyses will be included: (1) only the first event will be counted for each patient and all recurrent events will not be included, and the denominator for the calculation of percentages will be the number of patients at risk at the beginning of the time interval who did not experience a first event in the preceding intervals; and (2) the recurrent events in subsequent intervals will be counted once for each patient in the numerator of the corresponding interval, and the denominator for the calculation of percentages will be the number of patients at risk at the beginning of the time interval.

A KM curve will also be provided by treatment group for the time to first documented symptomatic hypoglycemia during the on-treatment period.

The number (%) of patients with at least 1 documented symptomatic hypoglycemia during the on-treatment period, as well as the corresponding number of events, will be summarized as necessary by hour of the day for each treatment group, using the following hour intervals: $\geq 23:00$ to $<06:00$, $\geq 06:00$ to $<10:00$, $\geq 10:00$ to $<14:00$, $\geq 14:00$ to $<18:00$, $\geq 18:00$ to $<23:00$.

Similar analysis may be provided for severe symptomatic hypoglycemia as appropriate.

A listing of patients for all events reported on the dedicated eCRF “Symptomatic hypoglycemia” page will be provided and sorted by the following order: (1) patients with protocol defined symptomatic hypoglycemia including severe symptomatic hypoglycemia, documented symptomatic hypoglycemia, or probable symptomatic hypoglycemia (see [Section 2.1.4.1](#)); and (2) patients with symptomatic hypoglycemia not meeting protocol definition; and (3) patients with asymptomatic hypoglycemia.

